7.2 Study Agent

Human Cytomegalovirus pp65-lysosomal-associated membrane protein (pp65-LAMP) mRNA-pulsed autologous dendritic cells

DCs are potent immunostimulatory cells that continuously sample the antigenic environment of the host and specifically activate CD4+ and CD8+ T cells and B-cells [14, 15]. They are at the crossroads of many of the elegant networks of the immune system, and DCs represent the most promising contemporary biologic entity for realizing the promise of immunotherapy. Potent immune responses and encouraging clinical results have been seen in Phase I and II human clinical trials in systemic cancers[16-32].

Human *CMV* is an endemic β -Herpesvirus that does not usually cause significant clinical disease[33]. During primary maternal infection, however, human *CMV* can cause severe encephalitis in fetuses and lead to congenital brain defects. Human *CMV* disease is also a significant problem in immunocompromised adults such as organ transplant recipients or patients with AIDS[33]. Herpesviruses have also been implicated in a number of human malignancies including lymphoma, nasopharyngeal cancer, cervical cancer, and Kaposi's sarcoma[34, 35]. Recently, expression of proteins unique to human *CMV* has been reported within a large proportion of malignant tumors including colorectal carcinoma, prostate cancer, and malignant astrocytomas[36-38]. Universal detection of the human *CMV* immunodominant protein pp65, immediate early gene 1 protein (IE1), and several other early antigens was demonstrated using IHC in Grade II-IV astrocytomas[38]. Presence of the virus in these samples was confirmed with ISH, PCR for human *CMV*-specific glycoprotein B (UL55), electron microscopic detection of

intact virions[38], and direct detection of the virus from fresh operative samples in the shell vial assay (unpublished data). Human *CMV* antigens were not detected in surrounding normal brain samples, meningiomas, or brains affected by ischemia, Alzheimer's disease, paraneoplastic encephalitis, or *Cryptococcal* cerebritis.

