The presence of highly-immunogenic human *CMV* antigens within MGs affords a unique opportunity to target these tumors immunologically. There is a vast amount of experience with both the safety and efficacy of immunotherapy targeting human *CMV*[33], and the presence of this virus within brain tumors may allow this experience to be leveraged toward the effective eradication of MG expressing human *CMV* antigens. Adoptive T cell therapy has been used to safely and successfully protect against *CMV* reactivation in myelodepleted BMT patients [39-42]. In addition, T cell mediated immunotherapy has proven highly effective in the treatment of *CMV*-associated disease within the CNS[43] and in the treatment of acute *CMV* infections[40, 44]. Tumors associated with other human *Herpesviruses*, such as Epstein-Barr virus-associated lymphoma, including tumors within the CNS, have also been effectively treated and even large tumors have been cured by immunotherapy[45-50]. More recently, a vaccine directed against the potent viral antigens of human papilloma virus has also been shown to reduce the incidence of human papilloma virus-related cervical intraepithelial neoplasia in a prospective, randomized, double-blind trial[51].

The potential for non-specific targeting of normal tissues is thought to be minimal in seropositive patients. After initial infection, *CMV* establishes lifelong latency in the infected individual, with cells of the myeloid lineage constituting a major reservoir for persistence of the virus. Virus can be detected within myeloid progenitors in the bone marrow, with a small portion of these cells demonstrating viral DNA replication without any detectable gene expression[52, 53]. Also a small proportion (typically 1 in 1,000 to 1 in 10,000) of peripheral blood monocytes can be found to contain *CMV* DNA, while detection of viral RNA (gene expression) is not detected[54-56]

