8 OBJECTIVES AND ENDPOINTS

Table 1. Objectives and Endpoints

	Objective	Endpoint	Analysis
Key Primary	To examine the impact of Td pre-conditioning with or without basiliximab on survival	Median survival from randomization	See Section 15.5.1
Other Primary	To determine whether pre-conditioning of the vaccine site with Td toxoid systemically increases the migration of CMV pp65 RNA-pulsed DCs to site-draining inguinal lymph nodes	The percentage of ¹¹¹ In-labeled DCs reaching inguinal nodes will be calculated from the initial signal at the injection site in the groin to 48 hours after the 4 th vaccination	See Section 15.5.2
Other Primary	To examine the impact to Td pre-conditioning on survival among patients who are CMV positive	Median survival from randomization	See Section 15.5.3
Other Primary	To assess the impact of Td pre-conditioning on survival among patients who are CMV negative	Median survival from randomization	See Section 15.5.4
Key Secondary	To examine the impact of Td pre-conditioning with and without basiliximab on progression-free survival	Median progression-free survival from randomization	See Section 15.6.1
Other Secondary	To examine the impact of Td pre-conditioning at the vaccine site on progression-free survival among patients who are CMV positive	Median progression-free survival from randomization	See Section 15.6.2
Other Secondary	To examine the impact of Td pre-conditioning on progression-free survival among patients who are CMV negative	Median progression-free survival from randomization	See Section 15.6.3
Exploratory	To describe changes from baseline in immune response as measured by IFN γ ELISpot	Median change from baseline in ELISpot at each follow-up assessment	See Section 15.7
Exploratory	To assess T cell polyfunctionality when ELISpot results are positive	Proportion of patients with 1, 2 and 3 functions at each assessment	See Section 15.7
Exploratory	To describe changes in T _{Regs} over time	Median change from baseline in T _{Reg} levels at each follow-up assessment	See Section 15.7
Exploratory	To measure levels of CCL3 and other inflammatory soluble factors	Median change from baseline in CCL3 and other inflammatory soluble factors.	See Section 15.7

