15.1 Study Design Overview

This randomized phase II study will assess the impact of tetanus pre-conditioning on migration among newly diagnosed GBM patients who have undergone definitive resection and completed standard temozolomide and radiation treatment, as well as the impact of tetanus pre-conditioning and basiliximab together on survival. After completing standard of care radiotherapy with concurrent temozolomide, patients will be randomized to 1 of 3 treatment arms:

- Group I will receive DC vaccinations with *unpulsed DC pre-conditioning* prior to the 4th vaccination;
- Group II will receive DC vaccinations with *Td toxoid pre-conditioning* prior to the 4th vaccination; and
- Group III will receive *basiliximab infusions* prior to the 1st and 2nd DC vaccinations along with Td toxoid pre-conditioning prior to the 4th vaccination.

A permuted block randomization algorithm using a 1:1:1 allocation ratio will be used to assign patients to a treatment arm. Randomization will be stratified by CMV status (positive, negative), with the assignment to arms I and II being double-blinded (See Sections 9.1.1 and 9.1.7 for further details).

The study was initially activated with Groups I and II. However, approximately 2 months the study's initial activation, the study has been amended to include Group III.

Once accrual to Groups I and II are complete, a decision will be made concerning the accrual of additional patients to the Groups I and II in order to assess the impact of Td toxoid pre-conditioning within subgroups defined by CMV status. Options include continued accrual to both strata, accrual to only one stratum, or termination of accrual. Details are provided in Section 15.8.

Per Section 9.1, the study has been amended to terminate randomization to Group III. Rationale is provided in Section 9.1. Though randomization to Group III has been terminated, the analyses proposed for Group III will still be done even though the power of planned analyses will be greatly reduced due to a sample size smaller than anticipated within Group III.

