15.2 Analysis Sets

Subject to the availability of data, all randomized patients will be included in all analyses of correlative and efficacy endpoints.

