15.7 Exploratory Objectives

Changes from baseline in immune response as measured by ELISpot will be explored at each follow-up assessment and within each treatment group. Though analyses are exploratory, a Kruskal-Wallis will be used to compare treatment groups relative to maximum changes in ELISpot observed. A similar analysis will be conducted for levels of T_{Reg}, CCL3, and other

inflammatory soluble factors. Parametric analyses, such as an analysis of variance, may be used in lieu of a Wilcoxon test if underlying assumptions are satisfied.

When ELISpot results are positive, the extent of T cell functionality will be assessed. For each patient, the proportion of patients with 1, 2, and 3 functions will be determined. A negative ELISpot will be assumed to have 0 functions. Within each treatment group, changes from baseline in the percentage of patients with 0, 1, 2 and 3 functions will be explored Hotelling's T-test or a nonparametric equivalent. Additional statistical analyses may be conducted to changes in polyfunctionality, as well as to address other exploratory goals

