15.9.4 Other Primary Objective: Survival Among CMV Positive Patients

One of the other primary goals of this study is to determine whether Td pre-conditioning at vaccination #4 in conjunction with DC vaccination and temozolomide is worthy of investigation in a large phase III study among patients who are CMV positive. That assessment involves a comparison of survival in Groups I and II among patients who are CMV positive.

The sample size requirements needed to address this subgroup question are similar to those described for the key primary objective (Section 15.9.2). A 1-tailed logrank test will be conducted at the 0.15 level of significance. To have 90% power to detect a hazard ratio of 0.5, 45 deaths need to be observed within the two arms being compared[131].

As described in section 15.9.2, we anticipate that patients will be accrued to the study at the rate of 4 patients per month, with a randomization rate of 3.5 patients per month. We also anticipate that approximately 50% of patients will be CMV positive.

As described in Section 15.9.2, the study will randomize patients to one of two arms, and after amendment, it will randomize patients to one of 3 arms. If a decision is made to continue patient accrual (See Section 15.8), the study will randomize patients to either Group I or II. Tabulated below is the anticipated accrual and randomization rate for CMV positive patients within each arm during each period of accrual.

Table 6. Anticipated Accrual and Randomization Rate for CMV Positive Patients

# of Arms Accruing	Accrual Rate (Patients / Month / Arm)	Randomization Rate (Patients / Month / Arm)
2 arms	1	0.88
3 arms	0.67	0.58

At the time of the interim analysis, we anticipate that approximately 36 CMV positive patients will have been accrued, with half being assigned to Group I and half to Group II. If accrual to

the CMV positive patient subgroup is continued for an additional 16 months, we expect to accrue 32 additional patients to that subgroup of which 28 will be randomized to either Group I or II. After completion of extended accrual, an additional 12 months of follow-up are anticipated to observe approximately 45 events assuming the treatment-arm median survivals are 12 and 24 months.

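### Section 15.7 analyses the pp65 ELISpot change without the CMV stratum used at randomisation; if the change differs by serostatus, the pooled rank test loses power and the pooled median mixes two populations

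*Combined protocol and SAP*

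**What the plan says.** As background, Section 7.2 says that CMV "establishes lifelong latency in the infected individual".

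Section 15.1: "Randomization will be stratified by CMV status (positive, negative"; Section 9.1.1 confirms that the stratum is CMV serology. Section 15.9.4: "We also anticipate that approximately 50% of patients will be CMV positive". Section 15.2, subject to data being available: "all randomized patients will be included in all analyses of correlative and efficacy endpoints".

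For pp65 ELISpot, Table 1 (Section 8) lists the exploratory endpoint "Median change from baseline in ELISpot at each follow-up assessment". Section 15.7 adds "Changes from baseline in immune response as measured by ELISpot will be explored at each follow-up assessment and within each treatment group" and, for the between-arm test, "a Kruskal-Wallis will be used to compare treatment groups relative to maximum changes in ELISpot observed". It also tracks the percentage of patients with 0, 1, 2 or 3 T cell functions, scoring a negative ELISpot as 0. Serostatus is not named in any of these analyses. By contrast, OS and PFS each have planned CMV-positive and CMV-negative analyses (Sections 15.5.3, 15.5.4, 15.6.2 and 15.6.3).

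Section 15.1 keeps the Section 15.7 immune analyses after enrolment closed in April 2018, and warns that the survival comparisons may not reach their planned power.

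**The concern.** The assay counts T cells that respond to a CMV antigen, and CMV serology is the randomisation stratum. It is natural to ask whether patients with earlier CMV infection and patients without it show the same ELISpot change after vaccination. If they do not, two things follow.

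- **The test.** Stratified randomisation nearly balances serostatus across arms, so the spread between strata contributes almost nothing to the arm difference. An unstratified rank test still counts that spread as noise. It rejects less often than its nominal level and can miss a real Td effect.
- **The summaries.** One median per arm lies between two populations and depends on their mix. In the function analysis, a patient who is already ELISpot-positive at baseline cannot convert from 0. If baseline positivity goes with serostatus, a pooled shift blends new responses with boosted ones.

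With the survival comparisons possibly underpowered, the immune results carry more of the interpretation than first planned.

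**Working it through.** **The plan's own figures.** Section 15.9 sizes the survival comparisons (45 deaths) and migration (12 per arm). It gives no sample size, alpha, SD or power for ELISpot, so there is no ELISpot figure to reproduce.

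**Inputs from the documents.** 35 patients each in Groups I and II (Section 15.9; a goal, with no final number given), 9 in Group III (Section 9.1), about 50% CMV positive (Section 15.9.4), and a Kruskal-Wallis test (Section 15.7).

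**Assumed inputs.** Two-sided alpha 0.05; normal outcomes with SD 1 within stratum; a stratum difference in ELISpot change of *d* SD; a Td effect of 0.8 SD in both strata, chosen to give about 90% power at *d* = 0.

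**Tests compared.** Pooled: H = 12/[N(N+1)] × Σ n_j (mean rank_j − (N+1)/2)², referred to chi-square on k−1 df. Stratified: rank within each serostatus stratum, divide ranks by (n_s + 1), sum observed minus expected over strata to give U, and refer U′V⁻¹U to chi-square on k−1 df. With two arms this is the van Elteren test.

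**Hand check of the conservatism.** With a 50:50 mix the pooled variance is 1 + d²/4, but with balanced arms only the 1 enters the arm difference. For a mean-based test the true error at nominal 5% is about 2[1 − Φ(1.96 √(1 + d²/4))]:

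- d = 0.5: 1.96 × 1.031 = 2.02, error 0.043
- d = 1: 1.96 × 1.118 = 2.19, error 0.028
- d = 2: 1.96 × 1.414 = 2.77, error 0.006

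**Simulation, 35 v 35** (6,000 runs per cell; 18 seropositive in Group I, 17 in Group II):

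| d (SD) | Type I, pooled | Type I, stratified | Power, pooled | Power, stratified |
|---|---|---|---|---|
| 0 | 0.050 | 0.050 | 0.90 | 0.90 |
| 0.5 | 0.047 | 0.056 | 0.88 | 0.90 |
| 1 | 0.030 | 0.053 | 0.82 | 0.90 |
| 2 | 0.004 | 0.051 | 0.53 | 0.89 |

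The type I column agrees with the hand check. Pooled power is slightly understated, because the Td arm has one fewer patient from the higher-change stratum. With 18 seropositive in both arms, power is 0.84 v 0.89 at 1 SD (a re-run with 20,000 replicates) and 0.62 v 0.89 at 2 SD. The loss is therefore about 5 to 8 points at 1 SD and 27 to 36 points at 2 SD.

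**Three groups, 35/35/9** (closer to the written test): 0.86 v 0.86 at d = 0, 0.76 v 0.87 at 1 SD, 0.42 v 0.86 at 2 SD.

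**Other prevalence.** With 30% or 70% seropositive and d = 2, pooled power is 0.70 or 0.69, against 0.89 stratified.

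**Pooled median.** In a 50:50 normal mix it lies at d/2. At d = 0 it equals both stratum medians. At d = 1 it is the 69th percentile of one stratum and the 31st of the other; at d = 2, the 84th and 16th.

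**Does taking change from baseline remove the issue?** Only if vaccination adds the same number of spots whatever the baseline. Section 12.7.5 reports background-subtracted spot counts per million PBMC, on an absolute scale. Suppose the relative rise is identical in both strata, Td multiplies the rise by 1.8, and log-SDs are 0.5 (baseline) and 0.6 (rise), all assumed. A 3-fold baseline difference then gives 76% v 85% power, and a 10-fold difference 41% v 84%. Pooled type I error is 1.4% and 0.1%.

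**A setting that favours pooling.** If only seropositive patients benefit (by 1 SD), controls do not differ by stratum, and seronegative SD is 0.2, the pooled test has more power: 0.56 v 0.48. Changing only the stratum difference to 1 SD reverses this to 0.14 v 0.46.

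**The case against.** The strongest objection is that the premise is not in the documents. No section reports ELISpot values by serostatus, at baseline or after vaccination. A reader might infer from the latency text in Section 7.2 that seropositive patients enter with pp65 memory, that seronegative patients are naive, and hence that the pooled median describes neither group and the test does lose power. The documents do not support those as facts. Section 7.2 describes where the virus persists; it does not describe T cell responses. It also reports pp65 detection across Grade II–IV astrocytomas, and the title of one cited paper reports CMV DNA in most seronegative donors, so equating seronegative with naive is not secure. This part stands: the harm must be stated conditionally.

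Three other tempting readings also fail:

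- **Invalid test.** Type I error below nominal leaves the test valid. Nothing here produces false positives.
- **Median in a sparse region.** This needs a wide separation between strata. On a log scale with log-SD 0.8, a 50:50 mix peaks at its midpoint for 3-fold and 5-fold ratios, and dips there only at 10-fold.
- **Drift in the seropositive share over visits.** No section suggests it, and the between-arm test uses each patient's maximum change.

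It is also fair that the analysis is exploratory with no stated alpha, that Section 15.7 allows further analyses, that 35 per arm is a goal, and that stratifying is not uniformly better.

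None of this removes the core point. Baseline differences need not cancel on an absolute count scale. The setting that favours pooling is narrow. A serostatus split chosen after the data are seen is weaker than one written beforehand.

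**Conclusion.** The point holds in conditional form. Section 15.7 and Table 1 leave the randomisation stratum out of the pp65 ELISpot analyses. If the ELISpot change does not differ by serostatus, nothing is lost (0.90 v 0.90). If it does, the pooled test remains valid but becomes conservative. With 35 per arm the power loss is about 2 points at 0.5 SD, 8 at 1 SD and 36 at 2 SD, or somewhat less with serostatus exactly even across arms. The pooled median then mixes two populations.

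These sizes rest on assumed alpha, effect, spread and stratum difference; only the group sizes and the 50% share come from the documents, as planning values. This is a cheap improvement to an exploratory analysis and does not affect a primary conclusion.

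**What to change.** 1. In Section 15.7, stratify the planned rank test by CMV serology: a stratified Kruskal-Wallis across treatment groups, and a van Elteren test for Group II v Group I. If the permitted parametric alternative is used, include the stratum as a factor.
2. In Section 15.7 and Table 1, show ELISpot change and the 0/1/2/3-function distribution by serostatus within each arm, alongside the overall summary.
3. Date the change, and state whether immune data by arm had been seen.

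The cost is SAP wording and one table split. The stratum is needed to randomise, so it should already be recorded for each randomised patient. The downsides are small cells in the descriptive tables, especially in Group III with 9 patients, and a modest power loss in narrow settings such as an effect confined to one stratum with very unequal spread.

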7.2.1 Pre-Clinical Experience

In our laboratories and those of others, systemic immunization using DCs co-cultured with uncharacterized tumor homogenate[101], whole tumor RNA[102], unidentified peptides eluted from tumor cells by gentle acid washing[103], or a distinct peptide encompassing the tumor-specific EGFRvIII mutation[104] have been shown to induce humoral and cell mediated systemic immune responses and to prolong the survival of rodents with brain tumors.

In our laboratory[101], inbred VM/Dk mice received three or four weekly intraperitoneal injections of autologous bone marrow-derived DCs transiently co-cultured with tumor homogenate. The homogenate was derived from a syngeneic murine astrocytoma cell line derived from a spontaneously occurring astrocytoma in the inbred VM/Dk mouse strain. Splenocytes from mice immunized in this way were able, *in vitro*, to lyse the astrocytoma cell line that was used to generate the tumor homogenate. They were also able to lyse other astrocytoma cell lines derived from the same inbred mouse strain, but they had no effect against syngeneic fibroblasts. Similarly, these immunized mice also demonstrated a significantly increased antibody titer against the astrocytoma cell line used to generate the homogenate. In addition, mice immunized with DCs transiently co-cultured with tumor homogenate that were subsequently challenged with a lethal dose of this astrocytoma cell line intracerebrally were found to have a median survival >160% longer than those immunized with DCs cultured without tumor homogenate ($P=0.016$). In addition, 50% of the mice treated with the tumor homogenate-supplemented DCs survived long-term without any evidence of tumor growth and also survived a rechallenge of tumor cells indicating that a sustained antitumor immune response had been established. These findings are especially significant in light of the fact that the astrocytoma cell line used is known to secrete the immunosuppressive agent TGF- β which is secreted by most human gliomas[105-109].

In another report from our laboratory[102], C57BL/6 mice received three weekly intraperitoneal injections of autologous bone-marrow derived DCs co-cultured with tumor homogenate or whole tumor RNA derived from the poorly immunogenic B16F10 melanoma cell line. Standard *in vitro* cytotoxicity assays again revealed that splenocytes harvested from mice immunized with DCs transiently co-cultured with either tumor-derived homogenate or whole tumor RNA were able to lyse B16F10 melanoma cells but not unrelated tumor cells from the same MHC background. In this experiment, mice immunized with autologous bone-marrow derived DCs co-cultured with tumor homogenate or whole tumor RNA increased median survival by >233% ($P=0.0006$) and 48% ($P=0.0001$), respectively, relative to mice immunized with DCs co-cultured with tumor homogenate or whole tumor RNA derived from an unrelated tumor with the same MHC background. In addition, 8/13 (61.5%) in the specific homogenate group and 4/10 (40%) in

the specific RNA group survived beyond the endpoint of the study without evidence of tumor. Immunization of mice with pre-existing tumors with specific tumor homogenate also demonstrated the potency of this immunization approach by increasing survival by 62.5% relative to controls. In these mice an inflammatory infiltrate composed of mononuclear cells and polymorphonuclear leukocytes was identified only in mice treated with DCs co-cultured with tumor homogenate that matched the intracerebral tumor challenge.

In a recent report from another laboratory[103], the survival of tumor-bearing rats injected subcutaneously with autologous bone marrow-derived DCs co-cultured with peptides eluted from tumor cells with a gentle acid wash was significantly prolonged compared to tumor-bearing rats receiving equivalent numbers of DCs co-cultured with peptides acid-eluted from normal astrocytes ($P < 0.05$). Median survivals in these groups were 35 and 22 days respectively. In addition, three of the twelve rats (25%) treated with DCs co-cultured with acid-eluted tumor peptides remained alive at the end of the experiment. In addition, immunohistochemical analysis of five animals from each group in this experiment documented an increased peritumoral and intratumoral infiltration of CD8⁺T cells, and to a lesser extent CD4⁺ T cells and macrophages, in the group treated with DCs co-cultured with peptides acid-eluted from tumor cells when compared to controls.

Inhibition of T_{Reg} Function with Anti-CD25-specific Monoclonal Antibodies

We have reported that our murine model of glioma indeed recapitulates MG-induced changes to the human peripheral blood CD4 and T_{Reg} compartments. Specifically, tumor-bearing mice exhibit CD4 lymphopenia, while CD4⁺CD25⁺Foxp3⁺GITR⁺ T_{Regs} come to represent an increased fraction of the peripheral blood CD4⁺ T cells that remain, despite themselves being reduced in number. Extending study to other sites, similar phenomena are observed in the spleens and CLN, while the reverse scenario emerges in bone marrow.

We employed this model to investigate the *in vivo* effects of T_{Reg} removal on anti-glioma immune responses. The current doctrine is that effective depletion of T_{Regs} may be achieved simply by systemic administration of anti-CD25 mAb[110, 111]. Likewise, in peripheral, non-CNS tumor models, the administration of anti-CD25 mAb has been employed in attempts to remove T_{Regs} and has effectively elicited prolonged survival to subcutaneous tumor challenge[112-114]. These studies, however, predated our ability to examine Foxp3 expression in T_{Regs} with antibody staining.

Following *in vivo* administration of anti-CD25 mAb (PC61), we discovered that CD4⁺Foxp3⁺GITR⁺ cells failed to entirely disappear, despite the present thinking. Instead, they persisted at significant levels in all sites tested. When isolated based on CD4 and GITR expression, however, these cells demonstrated none of the typical suppressive capacities of CD4⁺CD25⁺GITR⁺ T_{Regs} *in vitro*. Accordingly, systemic anti-CD25 mAb proved capable of enhancing T cell proliferation, IFN- γ production and glioma-specific CTL responses in treated mice. These effects translate to spontaneous tumor rejection in a murine model of established intracranial glioma (Figure 3).

Furthermore, when combined with a DC-based immunization strategy, anti-CD25 mAb elicited glioma rejection in 100% of challenged mice without attendant induction of EAE[115, 116]. Systemic anti-CD25 mAb administration therefore appears to counter the suppressive effects of

T_{Regs} without comprehensively eliminating the cells in vivo. This activity proves permissive for potent antitumor immunity in a murine glioma model that aptly recapitulates tumor-induced changes to the CD4 and T_{Reg} compartments.

[figure not shown]

Figure 3. PC61 in vivo extends survival and permits tumor rejection in a murine model of intracranial glioma. A. VM/Dk mice (n=10 per group) received i.p. PC61 or isotype control on Day -4. On Day 0, all mice were challenged intracranially with 10,000 syngeneic SMA-560 astrocytoma cells. Anti-CD25 produced 50% long-term survivors with no evidence of tumor. Differences in survival curves are significant (p=0.0002). B. Effects of PC61 in a therapeutic model. Treated mice (n=7) received i.p. PC61 three days following tumor implantation, when tumor was established. PC61 significantly extended median survival (p=0.0003) and produced nearly 15% long-term survivors with no evidence of tumor. C. Combination of anti-CD25 and DC vaccine produce 100% survival following intracranial tumor challenge. VM/Dk mice (n=5 per group) were administered 0.5 mg PC61 (anti-CD25) or isotype control antibody i.p. on Day -10. On Day -7, mice were vaccinated with 2.5x10⁵ DC electroporated with total tumor RNA from the SMA-560 glioma cell line or injected with an equivalent volume of PBS. Injections were delivered s.c. at the base of each ear. On Day 0, all mice were challenged i.c. with 10,000 syngeneic SMA-560 cells. Kaplan-Meier survival data are presented as the percentage of mice surviving in each group. Differences in survival were determined by log rank test. Anti-CD25 (p=0.0198) and DC vaccine (p=0.0153) alone each produced significant survival benefits, but the combination of the two elicited 100% long-term survival (p=0.0018).

